3.4 Primary outcome definition

The primary outcome is the simplified International Index of Erectile Function (IIEF-5, Rosen 1999), at 12 months. The IIEF-5 is also known as the Sexual Health Inventory for Men (SHIM).

The questionnaire used in the study was based on the 15-item British Association of Urological Surgeons (BAUS) version of the IIEF (see Appendix 6.1).

The IIEF-5 score is obtained by summing the scores to the questions 2, 4, 5, 7 and 15, as described in Appendix 6.1.

The IIEF-5 score ranges from 1 to 25, with a higher score indicating better erectile function.

Handling of partially complete IIEF-5

For participants who answered at least half of the questions, we will replace any of the missing answers by the lowest score (0 for questions 2, 4, 5, and 7, and 1 for question 15), thus returning a conservative total score. For participants with 3 or more missing responses, we will consider the IIEF-5 score as missing.

This IIEF-5 definition will be also applied at baseline, visit 2 and visit 3.

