### 7.2 Outcome endpoints

#### 7.2.1 Primary

Comparison of the proportion of men who recover erectile function at 12 months allocated to the NeuroSAFE intervention versus the control arm. Erectile function is measured using the IIEF-5 patient reported outcome questionnaire, where recovered function is defined as a score of 21 or more.

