Inclusion criteria	
 - Men opting to undergo RARP for organ confined prostate cancer (including radiological t3a). - Potent men (IIEF score of 22-25 on the first 5 questions of the IIEF-15 without any erectile function medical assistance) - Men who are continent of urine (no self-reported urinary incontinence) - Has given written informed consent - Ability to read English sufficiently to answer questionnaires and understand PIS

Exclusion criteria	
 - Unable to undergo RARP - Known overactive bladder - Any previous treatment for prostate cancer - Previous/current hormone treatment for prostate cancer - Nerve sparing deemed futile due to locally advanced disease by surgeon and radiologist
Number of sites	5
Study setting	Secondary care
Date of First Enrolment	10.10.18
Target Sample Size	Patient recruitment target in protocol: 404 patients Loss of follow-up: 10%
Primary Outcome	
 - IIEF-5 score at 12 months
Secondary Outcomes	
 - ICIQ at 3 months - ICIQ at 6 months - IIEF-6 at 12 months
Descriptive outcomes	
 - Time to erectile function recovery - Time to continence recovery - Positive surgical margins - Oncological outcomes at 12 months

1.2 *Objectives*

[figure not shown]

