4.1.2 Handling of missing data

Frequency of missing data will be reported descriptively, as explained in section 4.6. We will explore baseline characteristics associated with missingness, using logistic regression on missing IIEF-5 at 12 months as outcome.

Handling of partially incomplete variables

In section 3.3 (Time points and dates), 3.4 and 3.5 (Outcomes), we explain how we will handle some of the partially missing observations. For example, if participants have responded at least 3 or the 5 IIEF-5 questions, we will replace the missing questions by 0 to obtain a conservative IIEF-5 score. These ad-hoc imputations when constructing the variables are all described in the outcome definition, in section 3

Handling of missing baseline covariates

For the outcomes adjusted analysis, if some of the baseline adjustment covariates (site, age, baseline IIEF-5, ICIQ or IIEF-6) are missing we will impute them using mean or mode imputation (White, 2005).

Missing outcomes

The main analysis (of the primary and secondary outcomes) will be based on all available data, under the missing-at-random assumption, i.e. that the probability of being missing is independent of the unobserved outcome, conditionally on the observed data in the model (arm and baseline covariates). Sensitivity analysis under different assumptions will be conducted, as described in 4.11.

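### The SAP scores blank IIEF-5 items at the floor at baseline too, which puts false low outliers into a primary-model covariate; precision cost about 1% or less, no bias

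*SAP*

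**What the plan says.** SAP 3.4 forms the IIEF-5 by "summing the scores to the questions 2, 4, 5, 7 and 15" and states that "The IIEF-5 score ranges from 1 to 25". If at least half the items are answered, the plan is to "replace any of the missing answers by the lowest score (0 for questions 2, 4, 5, and 7, and 1 for question 15"); the stated reason is that the total is then conservative. With three or more blanks the score is missing. The rule is not confined to follow-up: "This IIEF-5 definition will be also applied at baseline, visit 2 and visit 3". SAP 3.5.2 handles the IIEF-6 in the same way, baseline included, when at least three of six items are answered.

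SAP 4.7 puts baseline IIEF-5 into the primary model as a linear term. SAP 4.1.2 replaces a missing baseline covariate by its mean or mode. The same section restates the floor rule as "we will replace the missing questions by 0 to obtain a conservative IIEF-5 score", without the exception for Q15.

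Entry required an "IIEF score of 22-25 on the first 5 questions of the IIEF-15" (SAP 1.1). Protocol 8.2 lets that score come from the baseline questionnaire or from clinical notes. SAP 3.6.1 labels 22 to 25 as no ED, 17 to 21 as mild and 12 to 16 as mild to moderate, and counts a score of 15 or more as recovery. In Protocol 7.2.1, "recovered function is defined as a score of 21 or more".

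**The concern.** A conservative score has a meaning for an outcome. It has none for a covariate measured before randomisation, where the aim is the most accurate value. Flooring a skipped item gives a man recruited as potent a baseline score in an ED category. The rules also invert the information: a man with one blank gets a value that is certainly too low unless his true answer was the floor, while a man with three blanks gets the sample mean.

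At stake at baseline is the quality of the adjustment. If most men lie within a few points of each other, a few false low scores have high leverage and flatten the fitted slope.

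At 12 months the same rule sets the primary outcome itself. The questionnaire in SAP Appendix 6.1 has explicit options for no sexual activity or no attempt at intercourse on Q2, Q4, Q5 and Q7, so a blank need not mean that. Whether the rule is conservative for the comparison between arms depends on who leaves items blank. None of the sensitivity analyses in SAP 4.11 varies the item rule.

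**Working it through.** **Inputs from the documents.** Five items, each with a maximum of 5; minimum 0 for Q2, Q4, Q5 and Q7, and 1 for Q15; the floor rule applies with one or two blanks; 364 evaluable men (SAP 1.4).

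**The plan's own range.** Minimum 0+0+0+0+1 = 1; maximum 5×5 = 25. The stated 1 to 25 is reproduced.

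**Highest score under the floor rule**

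| Blank items | Sum | Maximum |
|---|---|---|
| One of Q2, Q4, Q5, Q7 | 4×5 + 0 | 20 |
| Q15 | 4×5 + 1 | 21 (20 under the wording of 4.1.2) |
| Two, not Q15 | 3×5 + 0 + 0 | 15 |
| Two, one of them Q15 | 3×5 + 0 + 1 | 16 (15 under the wording of 4.1.2) |

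There are 56 sets of complete answers that total 22 to 25. Blanking one item in each gives 56×5 = 280 cases, all scoring 17 to 21 (1 to 5 points lost). Blanking two gives 56×10 = 560 cases, all scoring 12 to 16 (6 to 10 points lost). None reaches 22.

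**Effect on the baseline slope.** Assumptions, none of them given in the documents: true baseline uniform on 22 to 25 (mean 23.5, variance 1.25), true slope 1.0, residual SD 7, a proportion p of partial forms, blanks at random.

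- Mean item score: 23.5/5 = 4.7. Mean loss with one blank: (4×4.7 + 3.7)/5 = 4.5. With two blanks: 9.0.
- Approximate slope = V/(V + E), where V is the baseline variance and E the variance of the scoring error.
- One blank each: E = p(1−p)×4.5². For p = 1%, 3%, 5%, E = 0.200, 0.589, 0.962. The slope is 1.25/1.450 = 0.86, 1.25/1.839 = 0.68, 1.25/2.212 = 0.57.
- Half with two blanks: E = p×(0.5×4.5² + 0.5×9²) − (6.75p)². E = 0.502, 1.478, 2.417. The slope is 0.71, 0.46, 0.34.

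Simulation of 364 men agrees: about 0.87, 0.70 and 0.56 with one blank, and 0.74, 0.47 and 0.35 when half have two. Under mean imputation the slope stays close to 1.0.

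**A wider baseline.** If the baseline SD were 2.5 (V = 6.25), the formula at p = 3% gives 6.25/6.839 = 0.91 and 6.25/7.728 = 0.81. A simulation with such a baseline gave 0.76 to 0.88. Either is much milder than 0.68 and 0.46.

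**Effect on the treatment comparison.** Residual variance is 49 with a perfect covariate and 49 + 1.25×(1 − slope) with the degraded one. At a slope of 0.34 this is 49.825, so the SE ratio is √(49.825/49) = 1.008. Dropping the covariate altogether would give √(50.25/49) = 1.013. In simulation with a true effect of 2.0, the mean estimate stayed at 1.97 to 2.02. The SE was 0.734 to 0.736 with mean imputation and 0.736 to 0.741 with the floor rule.

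**Follow-up.** A man who answers 5 to everything he completes scores 20 or 21 with one blank and 15 or 16 with two; prorated (mean of answered items × 5) he scores 25. One blank costs at most 5 points and two at most 10. If the share of one-blank forms differed between arms by 5 percentage points (assumed), the mean difference would shift by at most 0.05×5 = 0.25 points; for two-blank forms, 0.05×10 = 0.5 points.

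**The case against.** The strongest reply is that nothing the SAP reports changes materially. Baseline IIEF-5 is there only for precision, its slope is not interpreted, and the error is independent of arm. That is correct, and it limits the point to a small improvement. The slopes also rest on assumed rates and an assumed mix of one and two blanks, so only a range can be given.

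The comparison with 22 to 25 is not item for item. Entry used Q1 to Q5, or clinical notes, while the SAP score uses Q2, Q4, Q5, Q7 and Q15. A complete SAP baseline score can itself fall below 22, and the real spread may exceed the eligibility range. This stands too.

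The floor rule at 12 months is prespecified with a reason, and prorating has its own weakness: skipped intercourse items may not resemble the answered ones. Patients are blinded to allocation, and nothing shows that item non-response differs by arm. This argues against replacing the primary score. It does not defend the rule at baseline, where the reason given does not apply.

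A reader might infer three stronger things that the documents do not support:

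- **Eligibility was decided with floored scores.** Nothing says so.
- **The rule stops recovered men being counted as recovered.** One blank rules out the descriptive no-ED class, and usually the protocol's threshold of 21. The SAP's threshold of 15 stays within reach, and the primary analysis is a mean difference on the continuous score.
- **Wholly missing forms are handled only as missing at random.** SAP 4.11.2 adds a not-at-random analysis.

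**Conclusion.** The point holds as a minor one. Under SAP 3.4, every baseline IIEF-5 that the floor rule scores lies at or below 21, and at or below 16 with two blanks; this is exact arithmetic. The consequence is a weaker baseline adjustment, with no bias in the treatment effect. The slope falls from 1.0 to somewhere between about 0.87 and 0.35 if 1% to 5% of forms are partial and true baseline scores lie within 22 to 25, and falls less if they are more spread out. The treatment SE rises by about 1% or less. The rate of partial forms, the true slope and the residual SD are all assumptions.

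At 12 months the rule could shift the arm difference only in so far as item non-response differs by arm or by level of function. That cannot be sized from the documents, and it justifies a sensitivity analysis and no more. The two statements of the Q15 floor disagree by one point and need reconciling whatever else is done.

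**What to change.** 1. **Baseline (SAP 3.4 and 3.5.2).** Limit the floor rule to follow-up visits. Treat a partly completed baseline IIEF-5 or IIEF-6 as missing and use the mean imputation already in 4.1.2. This has no real downside.
2. **12 months (SAP 4.11).** Keep the floor rule for the primary analysis. Add one sensitivity analysis that prorates the IIEF-5 when at least three of five items are answered, and report the number of partly completed forms by arm and visit. Prorating is less conservative for men who skip intercourse items, which is why it belongs in a sensitivity analysis.
3. **SAP 4.1.2.** Restate the floor as 0 for Q2, Q4, Q5 and Q7 and 1 for Q15, so that it matches 3.4.

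The cost is a few lines of SAP text and scoring code, best settled before the SAP is published and the data unblinded. After that, SAP 2.1 still allows limited and justified changes, which should be labelled as such.

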3.5 Secondary outcomes definition

3.5.1 ICIQ

Incontinence was assessed using the International Consultation on Incontinence Questionnaire (ICIQ) (Avery, 2004).

The ICIQ score is obtained by summing the questions 3, 4 and 5 of the ICIQ questionnaire (see appendix 6.3).

The ICIQ score ranges from 0 to 21, with higher scores representing worse incontinence.

Handling of partially complete ICIQ

Any missing question 3 or 4 will not be imputed. For participants with missing question 5, if their answer was 0 ("Never leaks urine") at question 3 and 4, we assumed the answer at question 5 was 0 ("Not at all").

Other partially complete response will not be imputed, and total ICIQ score considered as missing.

This ICIQ score definition will be applied at baseline, visit 2, visit 3 and visit 4.

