3.6.3 Urinary continence recovery

Urinary continence recovery (binary outcome) will be defined at each time-point, based on whether the ICIQ score is less or equal to 5.

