6.3 ICIQ scoring

ICIQ	
Q3	How often do you leak urine? 0 never 1 about once a week or less often 2 two or three times a week 3 about once a day 4 several times a day 5 all the time
Q4	We would like to know how much urine you think leaks. How much urine do you usually leak (whether you wear protection or not)? 0 none 2 a small amount 4 a moderate amount 6 a large amount
Q5	Overall, how much does leaking urine interfere with your everyday life? Please ring a number between 0 (not at all) and 10 (a great deal)

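### The ICIQ scoring rule sets to missing a man who answers that he never leaks but leaves the amount item blank, although his total is 0 by the meaning of the items

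*SAP*

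**What the plan says.** SAP 3.5.1 sums items 3, 4 and 5 of the questionnaire: "The ICIQ score ranges from 0 to 21, with higher scores representing worse incontinence". SAP appendix 6.3 gives the wording and codes of the two leakage items: "How often do you leak urine? 0 never" and "How much urine do you usually leak (whether you wear protection or not)? 0 none". Item 5 is rated from 0 to 10.

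For partial forms, SAP 3.5.1 has three rules:

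- Items 3 and 4: "Any missing question 3 or 4 will not be imputed".
- Item 5, when the man scored 0 "at question 3 and 4, we assumed the answer at question 5 was 0".
- Everything else: "Other partially complete response will not be imputed, and total ICIQ score considered as missing".

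The rules apply at baseline and at visits 2, 3 and 4. SAP 3.2 names ICIQ at 3 months as the main secondary outcome, and SAP 4.8 analyses it as a continuous score by linear regression in men with data available. SAP 4.1.2 assumes outcomes are missing at random given arm and baseline covariates. SAP 4.11 plans missing-data sensitivity analyses for the primary outcome only.

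The binary continence indicator (SAP 3.6.3) is "based on whether the ICIQ score is less or equal to 5", so it inherits any missing total. The SAP treats it as descriptive. In protocol 7.2.2.1, the proportion of men at or below 5 at 3 months is the urinary continence endpoint.

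**The concern.** The SAP already accepts that a man who never leaks has no interference from leakage, and fills item 5 for him. That never leaking means leaking no amount follows at least as directly, yet the SAP refuses to fill item 4. It is readier to fill gaps elsewhere. It gives the lowest score to up to two blank items of five on the IIEF-5 (3.4) and three of six on the IIEF-6 (3.5.2), where the true answers are unknown, and it infers earlier missing PSA values from a later one (3.6.5).

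The men lost this way all sit at the best end of the ICIQ scale. If the arms differ in the share of men who never leak, dropping some of these men changes the arm means by different amounts, and the regression cannot recover this from age, site and baseline score. A genuine early continence benefit could be understated, with no ICIQ sensitivity analysis to show it.

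**Working it through.** **1. What the rule does to each partial form.** Item 3 has 6 possible answers (0 to 5), item 4 has 4 (0, 2, 4, 6) and item 5 has 11 (0 to 10). Allowing a blank for each gives 7 × 5 × 12 = 420 forms. Removing the 6 × 4 × 11 = 264 complete forms and the one fully blank form leaves 155 partial patterns. The SAP scores one of them (0, 0, blank) and sets 154 to missing. These are counts of possible patterns, not of patients.

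| Item 3 | Item 4 | Item 5 | SAP total | Total by meaning |
|---|---|---|---|---|
| 0 | 0 | blank | 0 | 0 |
| 0 | blank | blank | missing | 0 |
| 0 | blank | 0 | missing | 0 |
| 4 | 2 | blank | missing | unknown, 6 to 16 |
| blank | 0 | 0 | missing | 0 to 5 by arithmetic |

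Rows 2 and 3 are the defect for the main secondary outcome. Rows 4 and 5 matter only for the indicator at 5 or less. Among the 154 unscored patterns, 95 already sum to 6 or more (not continent whatever the blank is) and one cannot exceed 5 (row 5). In the 95, the possible total still spans 5 to 15 points, so the continuous score is not known.

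**2. Size of the effect on the 3-month score.** The documents give no item-skip rate, never-leak rate or mean score, so every input here is an assumption except 182 men per arm (364 evaluable, SAP 1.4). Let q be the never-leak rate in an arm, m the mean score among leakers (same in both arms), and k the share of never-leakers who leave item 4 blank (same in both arms).

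- Mean with all men kept: (1 − q) × m
- Mean under the SAP rule: (1 − q) × m / (1 − qk)
- Ratio of observed to true difference: (1 − k) / [(1 − q₀k)(1 − q₁k)], where q₀ is control and q₁ is NeuroSAFE; m cancels
- Men lost: 182 × k × (q₀ + q₁)

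Illustration A: q₀ = 20%, q₁ = 30%, m = 7. True means are 5.6 and 4.9, difference 0.70. At k = 10% the observed means are 5.6/0.98 = 5.714 and 4.9/0.97 = 5.052.

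Illustration B: q₀ = 20%, q₁ = 35%, m = 10. True means are 8.0 and 6.5, difference 1.50.

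| Skip rate k | A: difference | A: attenuation | B: difference | B: attenuation | Men lost (A / B) |
|---|---|---|---|---|---|
| 0 | 0.70 | 0 | 1.50 | 0 | 0 / 0 |
| 2% | 0.69 | 1% | 1.49 | 1% | 2 / 2 |
| 5% | 0.68 | 3% | 1.46 | 2% | 5 / 5 |
| 10% | 0.66 | 5% | 1.43 | 5% | 9 / 10 |
| 20% | 0.62 | 11% | 1.34 | 10% | 18 / 20 |
| 30% | 0.57 | 18% | 1.25 | 17% | 27 / 30 |

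**3. How far this depends on the assumptions.** With never-leak rates of 10% and 20%, a 30% skip rate gives a ratio of 0.7/(0.97 × 0.94) = 0.768, or 23% attenuation. With 30% and 45% it gives 0.7/(0.91 × 0.865) = 0.889, or 11%. The ratio is below 1 whenever q₀ + q₁ − q₀q₁k is below 1, which covers every case above. If most men in both arms never leaked, the effect would reverse: with 60% and 70% and k = 30%, the ratio is 0.7/(0.82 × 0.79) = 1.08. If q, k and m are the same in both arms, both means shift equally and the bias is zero.

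**The case against.** The strongest reply is that the pattern may hardly occur. Item 4 has an explicit zero option, so a dry man has a box to tick. Protocol 7.2.1 says key questionnaires, including the 3-month ICIQ, have been administered by telephone, which may make skipping rarer. SAP 2.4 checks for missing data before analysis and refers problems to sites, SAP 4.6 reports missing-data frequencies, and SAP 2.1 allows limited, justified adjustments. Even at 10% to 30% skipping, illustration A loses only 0.04 to 0.13 points on a 0 to 21 scale. All of this stands as a limit on size. None of it changes the scoring rule, which still discards a score that follows from the man's own answer.

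Four stronger readings are tempting and are not supported:

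- *All never-leakers who skip follow-on items are lost.* Those who answer item 4 as 0 and skip only item 5 are kept.
- *Men whose continence status is settled have a known main secondary outcome discarded.* That outcome is the continuous score. With items 3 and 4 at 4 and 2 and item 5 blank, the total could be anything from 6 to 16. Only the descriptive indicator is settled.
- *The rule breaks missing at random.* Without a skip rate, one can say only that it may.
- *Baseline is materially harmed.* Entry requires no self-reported incontinence, so an imputed mean or mode should be near 0, and the variable is only a pre-surgery covariate.

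**Conclusion.** The point holds in a narrow form. SAP 3.5.1 sets to missing a man with item 3 at 0, item 4 blank and item 5 blank or 0, although his total is 0. If this occurs in practice, the loss is confined to men with score 0 and may violate the missing-at-random assumption for ICIQ at 3 months.

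Under the two main illustrations, the difference is attenuated by about 1% at 2% skipping and by 17% to 18% at 30%. These figures rest on equal skip rates and equal mean scores among leakers in both arms, and on assumed never-leak rates. Attenuation requires that those rates differ by arm and are not high in both. With equal skip rates, the rule would not by itself create a difference between arms with the same score distribution. The likely effect is small unless skipping is common. The case for change is that the SAP's own logic already covers these men and the correction is nearly free.

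**What to change.** In SAP 3.5.1, for all visits, replace the rule on items 4 and 5 with: *If item 3 is 0 and every other answered item is 0, blank item 4 and/or item 5 are set to 0. Forms with contradictory answers (item 3 at 0 with item 4 or 5 above 0) are queried and not filled.* The continuous total stays missing for all other partial forms. The condition on the other answers matters: a rule triggered by item 3 alone would also fill forms such as 0, 6, blank.

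Separately, for the descriptive indicator at 5 or less and for time to continence only, classify a partial form whenever its answered items settle the status in either direction: not continent if the minimum possible total is 6 or more, continent if the maximum possible total is 5 or less. Because 95 patterns settle as not continent and only one as continent, this step could add failures selectively, so report the indicator with and without these forms.

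Report by arm the number of forms completed by each rule, which will show whether the matter was of any consequence. The cost is a few sentences in the SAP and a few lines of code before unblinding, with no new data.

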3.5.2 IIEF-6

One of the secondary outcomes will be IIEF-6 at 12 months.

IIEF-6 score (Cappelleri J. C., 1999) will be derived by adding the scores to the question 1, 2, 3, 4 ,5 and 15 of the IIEF, as described in Appendix 6.2.

Handling of partially complete IIEF-6

The missing data will be handled similarly as the IIEF-5, replacing missing answers by the lower score for those completing at least 3 of the 6 IIEF-6 questions.

This IIEF-6 definition will be also applied at baseline, visit 2 and visit 3.

3.6 Descriptive outcomes definition

3.6.1 Erectile function recovery

Erectile function recovery (binary outcome) will be defined at each time-point, based on whether the IIEF-5 score is larger or equal to 15.

We will also report at each time-point the IIEF-5 as a categorical variable, as suggested in Rosen 1999: Severe (1-7), moderate (8-11), mild-moderate (12-16), mild (17-21), and no ED (22-25).

